6.2 Adverse Event Severity

The investigator will use the following definitions to rate the severity of each adverse event:

Mild	The adverse event is transient and easily tolerated by the subject.
Moderate	The adverse event causes the subject discomfort and interrupts the subject's usual activities.
Severe	The adverse event causes considerable interference with the subject's usual activities and may be incapacitating or life-threatening.

6.3 Relationship to Study Drug

The investigator will use the following definitions to assess the relationship of the adverse event to the use of study drug. Assessment of relatedness will be made with respect to the DAAs (ombitasvir/ABT-450/r and SOF) and with respect to RBV:

Reasonable Possibility	An adverse event where there is evidence to suggest a causal relationship between the study drug and the adverse event.
No Reasonable Possibility	An adverse event where there is no evidence to suggest a causal relationship between the study drug and the adverse event.

For causality assessments, events assessed as having a reasonable possibility of being related to the study drug will be considered "associated." Events assessed as having no reasonable possibility of being related to study drug will be considered "not associated." In addition, when the investigator has not reported a causality or deemed it not assessable, AbbVie will consider the event associated.

If an investigator's opinion of no reasonable possibility of being related to study drug is given, an "Other" cause of event must be provided by the investigator for the SAE.

[figure not shown]
6.4

Adverse Event Collection Period

All serious adverse events as well as protocol-related nonserious adverse events will be collected from the time the subject signed the study-specific informed consent until study drug administration. From the time of study drug administration until 30 days following discontinuation of study treatment has elapsed, all adverse events and serious adverse events will be collected, whether solicited or spontaneously reported by the subject. In addition, serious adverse events will be collected from the time the subject signed the study-specific informed consent until 30 days after the last dose of study drug.

Adverse event information will be collected as shown in [Figure 2](#).

Figure 2. Adverse Event Collection

6.5

Adverse Event Reporting

In the event of a SAE, whether associated with study drug or not, the Investigator will notify Clinical Pharmacovigilance within 24 hours of the site being made aware of the SAE by entering the SAE data into the electronic data capture (EDC) system. SAEs that occur prior to the site having access to the RAVE® system or if RAVE is not operable should be faxed to Clinical Pharmacovigilance within 24 hours of being made aware of the SAE.

Ombitasvir/ABT-450/Ritonavir
M14-567 Protocol
EudraCT 2014-003147-35

FAX to: [REDACTED]

6.6 Pregnancy

Subjects and their partners should avoid pregnancy and males should avoid sperm donation throughout the course of the study, starting with Study Day 1 and for 30 days after the end of treatment with DAAs only, or for 7 months after the last dose of RBV (or per local RBV label) and/or consistent with local treatment guidelines for RBV.

Pregnancy in a study subject must be reported to the AbbVie within 1 working day of the site becoming aware of the pregnancy. Subjects receiving a RBV-inclusive regimen who report a positive pregnancy test during the Treatment Period must be notified to stop RBV immediately. Administration of DAAs may be continued at the investigator's discretion, if the benefit of continuing therapy is felt to outweigh the risk (Section [5.4.1](#)).

Information regarding a pregnancy occurrence in a study subject and the outcome of the pregnancy will be collected for pregnancies occurring up to 30 days after the end of treatment with DAAs only, or 7 months (or per local RBV label) after the last dose of RBV for treatment with DAAs plus RBV. The investigator is encouraged to report the pregnancy information to the voluntary RBV Pregnancy Registry, if RBV is included within the regimen.

Subjects who discontinue study medications due to pregnancy will be monitored for SVR in the Post-Treatment Period as described in Section [5.1.3](#).

Pregnancy in a study subject is not considered an adverse event. However, the medical outcome of an elective or spontaneous abortion, stillbirth, or congenital anomaly is considered a serious adverse event and must be reported to AbbVie within 24 hours of the site becoming aware of the event.

6.7 Toxicity Management

For the purpose of medical management, all adverse events and laboratory abnormalities that occur during the study must be evaluated by the investigator. A table of Clinical Toxicity Grades for evaluating laboratory abnormalities is provided in [Appendix C](#). This

table should be used in determination of the appropriate toxicity management as discussed in [Section 6.7.1](#), [Section 6.7.2](#), [Section 6.7.3](#), [Section 6.7.4](#), [Section 6.7.5](#), and [Section 6.7.6](#).

A drug-related toxicity is an adverse event or laboratory value outside of the reference range that is judged by the investigator or AbbVie as having a "reasonable possibility" of being related to the study drug (Section 6.3). A toxicity is deemed "clinically significant" based on the medical judgment of the investigator. Laboratory abnormalities will be managed as deemed clinically appropriate by the investigator until resolved.

Investigators should avoid interrupting study drugs for more than 7 consecutive days. The Investigator should ensure that any study drug interruptions or RBV dose modifications and associated adverse events are promptly entered into the appropriate eCRFs.

The toxicity management guidelines below should be followed throughout the Treatment Period of the study.

6.7.1 Grades 1 or 2 Laboratory Abnormalities and Mild or Moderate Adverse Events

Subjects who develop a mild or moderate adverse event or Grade 1 or 2 laboratory abnormality, other than those discussed separately in Section 6.7.4 (Management of Decreases in Hemoglobin), Section 6.7.5 (Management of ALT Elevations), and Section 6.7.6 (Management of Creatinine Clearance), may continue study drugs with follow-up per study protocol and in accordance with local standard of care.

6.7.2 Grades 3 or 4 Laboratory Abnormalities

With the exception of Grade 3 or higher abnormalities of total bilirubin, uric acid, phosphorus, total cholesterol, triglycerides, or glucose (in subjects with a history of diabetes), if a subject experiences a Grade 3 or greater abnormal laboratory parameter during the Treatment Period, the abnormal laboratory test should be repeated. If the Grade 3 or greater abnormality is confirmed, the investigator should assess whether the abnormality can be managed medically without interruption of study drug, or whether

study drugs should be interrupted and the laboratory parameter followed until it improves. If study drugs are interrupted and restarted and the abnormality recurs, then study drugs should be permanently discontinued.

Decreases in serum hemoglobin or in calculated creatinine clearance, or elevations of serum ALT should be managed according to the guidance in Section 6.7.4, Section 6.7.5, and Section 6.7.6 below. Grade 3 or greater abnormalities of total bilirubin, uric acid, phosphorus, total cholesterol, triglycerides, or glucose (in subjects with a history of diabetes) should be managed medically as appropriate and do not require confirmation or study drug interruption unless deemed necessary by the investigator.

6.7.3 Severe Adverse Events or Serious Adverse Events

If a subject experiences a severe adverse event or a serious adverse event that the investigator considers to have a reasonable possibility of relationship to study drug, the investigator should assess whether the adverse event can be managed medically without interruption of study drug, or whether study drugs should be interrupted until it improves. If study drugs are interrupted and restarted and the adverse event recurs, then study drugs should be permanently discontinued.

If a subject experiences a severe adverse event or serious adverse event that is considered unrelated (no reasonable possibility) to the study drugs, it is not necessary to interrupt study drugs unless an interruption is required because of the nature of the event (e.g., unable to take oral medications). The investigator should ensure that all serious adverse events are reported to AbbVie within 24 hours of awareness. Serious adverse event follow-up information, including associated dose interruptions (or discontinuations), must be reported to AbbVie within 24 hours of awareness by entering updated SAE information into the appropriate eCRFs.

Severe adverse events and any associated dose interruptions (or discontinuations) should be promptly entered into the appropriate eCRFs.

6.7.4 Management of Decreases in Hemoglobin

For Subjects Not Receiving Ribavirin:

Hemoglobin decreases should be managed according to grade, based on the guidance in Section [6.7.1](#) and Section [6.7.2](#) above.

For Subjects Receiving Ribavirin:

Reductions in hemoglobin are a well characterized side effect of ribavirin exposure. If a subject receiving the standard dose of ribavirin experiences a hemoglobin decrease meeting one of the criteria outlined in [Table 9](#), a confirmatory test should be performed. If the hemoglobin decrease is confirmed, the management guidelines in [Table 9](#) should be followed. Management will be different for subjects without a history of known cardiac disease and subjects with known cardiac disease. Subjects experiencing decreases in hemoglobin that do not meet the criteria outlined in [Table 9](#) may need hemoglobin evaluations at more frequent intervals at the discretion of the investigator.

The dose of RBV should not be further modified in subjects with creatinine clearance < 50 mL/min who are receiving a reduced dose of RBV. Reductions in hemoglobin in these subjects should be managed as medically appropriate and as outlined in [Table 9](#).

Use of hematologic growth factors (such as erythropoietin or filgrastim) or blood transfusions are permitted at the discretion of the investigator. Management of hematologic growth factor therapy is the responsibility of the Investigator, and growth factors will not be provided by AbbVie.

Alternate management of hemoglobin decreases outside of these criteria is permitted with approval of the AbbVie Study Designated Physician.

Table 9.**Ribavirin Dose Modification Guidelines in Management of Hemoglobin Decreases**

Hemoglobin Value	Intervention
Subjects with Creatinine Clearance ≥ 50 mL/min	
< 10 g/L and ≥ 8.5 g/dL	Reduce RBV dose.* Study drugs may be continued. If hemoglobin increases to ≥ 10 g/dL, may increase RBV; with gradual dose increases in 200 mg increments towards original dose.
< 8.5 g/dL	Interrupt ribavirin. Manage the subject as medically appropriate. If hemoglobin increases to ≥ 8.5 g/dL, RBV may be restarted.
Additional Guidance for Subjects with History of Stable Cardiac Disease and Creatinine Clearance ≥ 50 mL/min	
Hemoglobin decrease of ≥ 2 g/dL during any 4-week treatment period	Reduce RBV dose.* If a subsequent hemoglobin result is greater than the level that triggered the dose reduction, RBV dose may be increased; with gradual dose increases in 200 mg increments.
< 12 g/dL after a 4-week RBV dose reduction	Interrupt ribavirin. Manage the subject as medically appropriate. If subsequent hemoglobin increases to ≥ 12 g/dL, RBV may be restarted.
For Subjects with Creatinine Clearance < 50 mL/min	
< 10 g/L	Interrupt RBV. Manage the subject as medically appropriate. If hemoglobin increases ≥ 10 g/dL, RBV may be restarted. If creatinine clearance increases to ≥ 50 mL/min, refer to guidance above.

* First dose reduction of ribavirin is by 200 mg/day. If needed, second dose reduction of ribavirin is by an additional 200 mg/day. Subjects whose dose of ribavirin is reduced to 600 mg daily receive one 200 mg capsule in the morning and two 200 mg capsules in the evening.

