5.2.3.3 Prohibited Therapy

Subjects must be able to safely discontinue any prohibited medications within 2 weeks or within 10 half-lives of the respective medication/supplement (if known), whichever is longer, prior to initial study drug administration through 2 weeks following discontinuation of study drugs. Subjects must be consented prior to discontinuing any prohibited medications for the purpose of meeting study inclusion criteria.

In addition to the medications listed in [Table 3](#), use of known strong inducers of CYP3A or strong inhibitors or inducers of P-glycoprotein is prohibited within 2 weeks of the respective medication/supplement prior to the initial dose of study drug through the first 2 weeks after the subject has completed study drugs.

Refer to the current local labels for ritonavir, RBV, and SOF for a list of prohibited medications. Anti-HCV medications other than those specified in the protocol will not be allowed during the treatment period of the study.

Contraceptives

Prior to enrollment, subjects should agree to practice two effective methods of birth control while receiving study drugs starting with Study Day 1 and for 7 months after stopping study drug or as directed by the local ribavirin label. Subjects using systemic estrogen-containing contraceptive therapy (including estrogen-containing oral contraceptives) have a higher risk for elevated ALT levels. Subjects using these medications must discontinue them at least 2 weeks prior to study drug administration or 10 half-lives (if known), whichever is longer. Subjects may replace the systemic

estrogen-containing contraceptive with a progestin-only hormonal contraceptive method. Estrogen-containing contraceptives may be resumed 2 weeks after the last dose of DAAs.

Use of hematopoietic growth factors is not permitted during this study without the approval of the AbbVie Study Designated Physician. Management of hematologic growth factor therapy is the responsibility of the investigator; growth factors will not be provided by AbbVie, and AbbVie will not reimburse for the expense of growth factors or their use.

Investigators should refer to the package inserts for erythropoiesis stimulating agents for additional information regarding their use.

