5.5 Treatments**5.5.1 Treatments Administered**

Each dose of DAA study drugs (ombitasvir/ABT-450/r and SOF) and RBV (if applicable) will be dispensed in the form of tablets. Study drugs will be dispensed at the visits listed in [Table 4](#).

Ombitasvir/ABT-450/r will be provided by AbbVie as 12.5 mg/75 mg/50 mg tablets. Ombitasvir/ABT-450/r will be taken orally as 2 tablets every morning which corresponds to a 25 mg ombitasvir/150 mg ABT-450/100 mg ritonavir dose QD.

SOF will be provided by AbbVie as 400 mg tablets. SOF will be taken orally as 1 tablet every morning, which corresponds to a 400 mg dose QD.

For subjects randomized to a RBV-inclusive regimen, RBV will be provided as 200 mg tablets during the Treatment Period. RBV should be dosed based on consideration of the subject's weight from Study Day 1, either 1000 mg or 1200 mg daily divided BID per local label (e.g., < 75 kg = 1000 mg daily divided BID or ≥ 75 kg = 1200 mg daily divided BID) and his/her hemoglobin test results from the Screening Visit, according to the current approved local RBV label.

For subjects with calculated creatinine clearance ≥ 30 to < 50 mL/min, RBV should be given as alternating daily doses of 200 mg and 400 mg as described in Section [6.7.6](#); [Table 9](#). Subjects will be instructed to take study medication at the same time(s) every day. All study drugs should be administered with food. Subjects will be instructed to bring in all bottles at each visit.

Following enrollment, the site will use the IRT system to obtain the study drug container numbers to dispense at the study visits specified in [Table 4](#). Study drugs must not be dispensed without contacting the IRT system, and only for subjects enrolled in the study through the IRT system. The site will also contact the IRT system to provide study drug return information for each container at the visits specified in [Table 4](#) (Section [5.5.7](#)).

At Study Day 1, subjects will be administered study drugs by the study site personnel and receive instructions for self-administration of all study drugs from Study Day 2 through the end of the Treatment Period.

All subjects who receive at least one dose of DAA who meet virologic failure criteria during treatment (Section 5.4.1.1) will be discontinued from treatment. Resistance monitoring will continue in the PT Period regardless of whether subjects opt for alternative post-study treatment.

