5.5.4 Selection and Timing of Dose for Each Subject

Study drug dosing will be initiated at the Study Day 1 Visit. Ombitasvir/ABT-450/r and SOF will be dosed QD. Thus with normal dosing, 2 ombitasvir/ABT-450/r tablets and 1 SOF tablet should be taken in the morning.

RBV (if applicable) should be dosed BID, e.g., 2 or 3 tablets taken in the morning, and 3 RBV tablets should be taken in the evening. Subjects with renal impairment should receive a reduced dose of RBV, as described below ([Table 8](#)).

Table 8. Recommended Ribavirin Dosing in Chronically HCV-Infected Patients with Chronic Kidney Disease

Renal Impairment and Creatinine Clearance, mL/min	Renal Severity	RBV Dose (mg/day)
Normal (> 80 mL/min)	None	1000/1200
CKD Stage 3 (30 – 50 mL/min)	Moderate	200 alternating with 400
CKD Stage 4 (< 30 mL/min)	Severe	200

Note: Brennan et al.²⁵

All study drugs should be dosed together and administered with food.

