6.7.6 Creatinine Clearance

If calculated creatinine clearance (by Cockcroft-Gault formula) is confirmed to have decreased to < 50 mL/minute (in a subject with a baseline creatinine clearance of ≥ 50 mL/min), or to below 30 mL/min (in a subject with baseline creatinine clearance < 50 mL/min), medical evaluation should include a full review of current medications, including those taken on an as needed basis, those which are sold over the counter and any dietary and herbal supplements, and appropriate dose reduction or discontinuation based on impaired renal function should be done (if applicable). Ribavirin dose should be adjusted as in [Table 10](#). Alternative management of RBV dose in the setting of reduced renal function will require approval of the AbbVie Study Designated Physician.

The investigator should also consider whether drug-drug interactions with concomitant medications may have contributed to the decrease in creatinine clearance, and whether discontinuation or substitution of the possible interacting drug might be considered. For example, drug interactions between DAAs and some antihypertensive medications could potentially increase exposures of the antihypertensive, which may lead to reduction in renal function. If anti-hypertensive medications are adjusted, vital signs should be

monitored to ensure appropriate blood pressure control. Refer to Section 5.2.3 for additional information regarding drug-drug interactions.

Table 10. Dosing of RBV in Subjects with Renal Impairment

CrCl Value	RBV Dose
30 – 50 mL/min	Alternating doses, 200 mg and 400 mg every other day
< 30 mL/min	200 mg daily
Hemodialysis	200 mg daily

Note: For RBV dosing in subjects with concurrent creatinine clearance < 50 mL/min and Hb < 10 (Table 8).

If creatinine clearance improves, the site should perform all necessary readjustments of any dose modifications that have been made. If creatinine clearance improves to above the level that triggered the RBV dose reduction, the RBV dose may be increased accordingly.

The investigator should ensure that any concomitant medication changes, RBV dose reductions, and study drug discontinuations, as well as consequent related adverse events are entered into the appropriate eCRFs.

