Appendix C. Clinical Toxicity Grades

Clinical Toxicity Grades for HCV Studies ^{1,2}				
	GRADE 1 TOXICITY	GRADE 2 TOXICITY	GRADE 3 TOXICITY	GRADE 4 TOXICITY
HEMATOLOGY				
ABSOLUTE NEUTROPHIL COUNT DECREASED	<LLN – 1500/mm ³ <LLN – 1.5 × 10 ⁹ /L	<1500 – 1000/mm ³ <1.5 – 1.0 × 10 ⁹ /L	<1000 – 500/mm ³ <1.0 – 0.5 × 10 ⁹ /L	<500/mm ³ <0.5 × 10 ⁹ /L
EOSINOPHIL COUNT INCREASED	650-1500 cells/mm ³	1501-5000 cells/mm ³	>5000 cells/mm ³	Hypereosinophilic
HEMOGLOBIN DECREASED	<LLN – 10.0 g/dL <LLN – 6.2 mmol/L <LLN – 100 g/L	<10.0 – 8.0 g/dL <6.2 – 4.9 mmol/L <100 – 80 g/L	<8.0 – 6.5 g/dL <4.9 – 4.0 mmol/L <80 – 65 g/L	<6.5 g/dL <4.0 mmol/L <65 g/L
INTERNATIONAL NORMALIZED RATIO (INR), INCREASED	>1 – 1.5 × ULN	>1.5 – 2 × ULN	>2 × ULN	
LYMPHOCYTE COUNT DECREASED	<LLN – 800/mm ³ <LLN × 0.8 – 10 ⁹ /L	<800 – 500/mm ³ <0.8 – 0.5 × 10 ⁹ /L	<500 – 200 mm ³ <0.5 – 0.2 × 10 ⁹ /L	<200/mm ³ <0.2 × 10 ⁹ /L
PLATELETS DECREASED	<LLN – 75,000/mm ³ <LLN – 75.0 × 10 ⁹ /L	<75,000-50,000/mm ³ <75.0 – 50.0 × 10 ⁹ /L	<50,000-25,000/mm ³ <50.0 – 25.0 × 10 ⁹ /L	<25,000/mm ³ <25.0 × 10 ⁹ /L
PTT	>1 – 1.5 × ULN	>1.5 – 2 × ULN	>2 × ULN	
WHITE BLOOD CELL COUNT DECREASED	<LLN – 3000/mm ³ <LLN – 3.0 × 10 ⁹ /L	<3000 – 2000/mm ³ <3.0 – 2.0 × 10 ⁹ /L	<2000 – 1000/mm ³ <2.0 – 1.0 × 10 ⁹ /L	<1000/mm ³ <1.0 × 10 ⁹ /L
WHITE BLOOD CELL COUNT INCREASED	10,800 – 15,000 cells/mm ³	>15,000 – 20,000 cells/mm ³	>20,000 – 25,000 cells/mm ³	>25,000 cells/mm ³
CHEMISTRIES				
ALBUMIN, SERUM, LOW	<LLN – 3 g/dL <LLN – 30 g/L	<3 – 2 g/dL <30 – 20 g/L	<2 g/dL <20 g/L	
BILIRUBIN, HIGH	>ULN – 1.5 × ULN	>1.5 – 3.0 × ULN	>3.0 – 10.0 × ULN	>10.0 × ULN
BUN	12.5-2.5 × ULN	>2.5 – 5.0 × ULN	>5 – 10.0 × ULN	>10 × ULN
CALCIUM, SERUM LOW	<LLN – 8.0 mg/dL <LLN – 2.0 mmol/L	<8.0 – 7.0 mg/dL <2.0 – 1.75 mmol/L	<7.0 – 6.0 mg/dL <1.75 – 1.5 mmol/L	<6.0 mg/dL <1.5 mmol/L
CALCIUM, SERUM HIGH	>ULN – 11.5 mg/dL >ULN – 2.9 mmol/L	>11.5 – 12.5 mg/dL >2.9 – 3.1 mmol/L	>12.5 – 13.5 mg/dL >3.1 – 3.4 mmol/L	>13.5 mg/dL >3.4 mmol/L
CALCIUM, IONIZED, LOW	<LLN – 1.0 mmol/L	<1.0 – 0.9 mmol/L	<0.9 – 0.8 mmol/L	<0.8 mmol/L
CALCIUM, IONIZED, HIGH	>ULN – 1.5 mmol/L	>1.5 – 1.8 mmol/L	>1.8 – 1.6 mmol/L	>1.8 mmol/L

Clinical Toxicity Grades for HCV Studies
v1.1; 08 June 2009

Clinical Toxicity Grades for HCV Studies (Continued)

	GRADE 1 TOXICITY	GRADE 2 TOXICITY	GRADE 3 TOXICITY	GRADE 4 TOXICITY
CHOLESTEROL HIGH	>ULN – 300 mg/dL >ULN – 7.75 mmol/L	>300 – 400 mg/dL >7.75 – 10.34 mmol/L	>400 – 500 mg/dL >10.34 – 12.92 mmol/L	>500 mg/dL >12.92 mmol/L

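### Table 9 prints two ribavirin haemoglobin triggers in the wrong unit, two cross-references name the wrong ribavirin table, and two sections give different growth-factor rules

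*Protocol*

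**What the plan says.** All of the points concern ribavirin management in the protocol.

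- **Table 9, clearance of 50 mL/min or more (Section 6.7.4).** The dose-reduction row applies at "< 10 g/L and ≥ 8.5 g/dL". Its recovery level is 10 g/dL, and the next row interrupts ribavirin below 8.5 g/dL.
- **Table 9, clearance below 50 mL/min.** The only row interrupts ribavirin below 10 g/L, then states "If hemoglobin increases ≥ 10 g/dL, RBV may be restarted".
- **Appendix C.** Grade 1 haemoglobin is given in parallel units: "<LLN – 10.0 g/dL <LLN – 6.2 mmol/L <LLN – 100 g/L".
- **Note under Table 10 (Section 6.7.6).** "For RBV dosing in subjects with concurrent creatinine clearance < 50 mL/min and Hb < 10 (Table 8"; no unit is given for haemoglobin. Table 8 (Section 5.5.4) sets dose by renal function only and lists "200 alternating with 400" mg/day for clearance of 30 to 50 mL/min.
- **Section 5.5.1.** For clearance of 30 to below 50 mL/min, "RBV should be given as alternating daily doses of 200 mg and 400 mg as described in Section" 6.7.6, followed by a citation of Table 9. The renal doses in Section 6.7.6 are in Table 10.
- **Growth factors.** Section 5.2.3.3: "Use of hematopoietic growth factors is not permitted during this study without the approval of the AbbVie Study Designated Physician". Section 6.7.4: "Use of hematologic growth factors (such as erythropoietin or filgrastim) or blood transfusions are permitted at the discretion of the investigator".

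Section 6.7.4 also says that subjects with clearance below 50 mL/min who are already on a reduced ribavirin dose should have no further modification, and then refers them to Table 9, whose instruction is to interrupt.

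**The concern.** Falling haemoglobin is the known ribavirin toxicity, and the protocol's Introduction says that declines in earlier studies were managed largely by reducing the ribavirin dose. That is the step whose trigger is misprinted. Section 6.7.4 also ties the confirmatory haemoglobin test to meeting a Table 9 criterion. Read literally, a value from 8.5 to below 10 g/dL in a subject with no cardiac criterion prompts neither a repeat test nor a dose reduction.

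The Table 10 note is the most consequential item, because its destination looks plausible. A reader who follows it for a subject with low clearance and low haemoglobin finds a continuing dose and nothing to signal that the applicable instruction is to stop. Such subjects can be enrolled, since only clearance below 30 mL/min is excluded, and clearance may also fall on treatment.

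On growth factors, a site that acts on 6.7.4 alone breaches 5.2.3.3.

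**Working it through.** **Units.** Appendix C gives each haemoglobin cut in both units: 10.0 g/dL = 100 g/L, 8.0 g/dL = 80 g/L, 6.5 g/dL = 65 g/L. The ratio is 10 each time, so 10 g/L = 10 / 10 = 1.0 g/dL.

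| Table 9 row | As printed, in g/dL | With g/dL in place of g/L |
|---|---|---|
| Clearance ≥ 50, reduce dose | < 1.0 and ≥ 8.5: empty | < 10 and ≥ 8.5: adjoins the < 8.5 row and matches the 10 g/dL recovery level |
| Clearance < 50, interrupt | < 1.0, restart at ≥ 10 | < 10, restart at ≥ 10 |

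The printed triggers are too low by a factor of 10 / 1.0 = 10. In the second row, the printed trigger lies far below the Grade 4 cut of 6.5 g/dL.

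**Cross-references.**

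| Where | Subject | Table cited | Content of that table | Correct table |
|---|---|---|---|---|
| Note under Table 10 | Clearance < 50 with Hb < 10 | Table 8 | Dose by renal function, no haemoglobin criterion | Table 9, clearance < 50 row: interrupt |
| Section 5.5.1 | Alternating 200/400 mg renal dose | Table 9 | Haemoglobin decreases | Table 10 |

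Both citations are one number too low.

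**Growth factors.** Section 5.2.3.3 requires approval from the sponsor's physician; 6.7.4 leaves the decision to the investigator and does not mention that approval. The closing sentence of 6.7.4, on alternate management, covers departures from the haemoglobin criteria and does not reconcile the two rules.

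**How often the rule would be needed.** Inputs: Arm B, about 10 subjects; Table 2 rates of haemoglobin below 10 g/dL on 12 weeks of 3-DAA + RBV, 5.5% (placebo-controlled pool) and 6.2% (regimen-controlled pool). With p the rate and n = 10:

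- Expected number, n × p: 10 × 0.055 = 0.55; 10 × 0.062 = 0.62.
- Chance of at least one, 1 − (1 − p)^n: 1 − 0.945^10 = 0.432; 1 − 0.938^10 = 0.473.

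These rates include values below 8.5 g/dL, for which Table 9 has a correctly printed row. The documents give no rate for low clearance together with low haemoglobin, so the Table 10 note cannot be quantified.

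**The case against.** The strongest reply is that these are self-correcting slips. Both affected rows print 10 g/dL as the recovery or restart level, and no clinician would wait for a haemoglobin of 1.0 g/dL. Sections 6.7.1 and 6.7.2 send haemoglobin decreases to 6.7.4, which deals with clearance below 50 mL/min and points to Table 9. Section 5.5.1 states the renal dose in its own sentence and cites the right section. Obtaining approval satisfies both growth-factor rules. The two wrong table numbers look like one renumbering slip. It can also be said that the criticism reads Table 9 literally for the units but by intent for the cross-reference.

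Most of this stands as a limit on impact. It does not remove the defect, because each reading leaves one: read literally, the dose-reduction trigger cannot fire; read as intended, the Table 10 note leads away from the interruption rule. The 43% to 47% is the chance that a subject has low haemoglobin, not the chance of mismanagement, and it rests on rates from genotype 1 subjects on a dasabuvir-containing regimen.

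The version also matters. This protocol describes about 20 subjects, while the SAP describes about 70, with ribavirin in Arms B, C, D and E. The documents do not show whether a later protocol corrected these points. If it did not, more subjects are exposed than Arm B alone.

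**Conclusion.** The concern holds on each element: two triggers in the wrong unit, two wrong table references and two differing growth-factor rules. As printed, the dose-reduction row is met by no haemoglobin value, and the only row for clearance below 50 mL/min triggers a factor of 10 too low. Assuming the Table 2 rates carry over to about 10 Arm B subjects, 0.55 to 0.62 subjects would be expected to fall below 10 g/dL. Practical harm is limited because the intent can be inferred. SVR12, sample size, the SAP's laboratory haemoglobin grades (Table 12, correctly in g/L) and its anaemia query are unaffected. The text should still be corrected, since safety dosing instructions should not depend on sites working out what was meant. The sentence in 6.7.4 on not modifying a renally reduced dose is a matter of clarity only; it most naturally means no further step-down, with interruption below 10 g/dL.

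**What to change.** - **Table 9:** change the unit of the 10 g/L limit to g/dL in both rows.
- **Note under Table 10:** specify haemoglobin below 10 g/dL and cite Table 9.
- **Section 5.5.1:** cite Section 6.7.6 and Table 10.
- **Growth factors:** state one rule in 5.2.3.3 and 6.7.4, for example sponsor-physician approval in both. Put blood transfusion in a separate sentence in 6.7.4 so that it stays at the investigator's discretion; 5.2.3.3 does not require approval for it.
- **Section 6.7.4, clearance below 50 mL/min:** say that the dose is not reduced further and that ribavirin is interrupted as Table 9 directs.

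If a later protocol version is in force, check it for the same text first. The cost is a few words in an administrative change or the next amendment, with no new data, visits or procedures.
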